4.1 Hypothesis

We hypothesize that BI patients will experience significant improvements in psychosocial functioning and better compliance compared to UC. As secondary outcomes, we will evaluate within group changes (BI group) from enrollment to completion of 4-month intervention program as well as outcomes in higher risk versus lower risk patients based on their initial preoperative psychosocial evaluations. We hypothesize that the BI group will display higher levels of dietary adherence and physical activity and attend more postoperative appointments, compared to UC.

4.2 Specific Aim 1

To assess the efficacy of a 4-month behavioral intervention (BI) program after bariatric surgery on psychosocial functioning compared to usual care (UC). Psychosocial outcomes assessed will be quality of life (primary), mood (depression/anxiety), eating behaviors, self-efficacy and interpersonal functioning using standardized measures.

4.3 Specific Aim 2

To evaluate the efficacy of a 4-month behavioral intervention program on postoperative dietary and lifestyle adherence compared to the UC.

4.4 Specific Aim 3

To assess the feasibility of a 4-month behavioral program in postoperative bariatric surgery patients. We will evaluate recruitment, attrition, safety and patient/provider satisfaction in the BI group.

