6 STUDY DESIGN

6.1 Description

This prospective, randomized pilot trial will evaluate a comprehensive postoperative behavioral support intervention using a 4-month bi-weekly program (BI group) in 40 bariatric surgery patients (all surgical procedure types) from the GHS Center for Nutrition and Weight Management (CNWM) compared to 40 usual care (UC) patients. Participants will be randomized to BI or UC using a computer program. Treatment will occur in two session periods to accommodate patients who complete surgery during the study duration.

We will recruit preoperative bariatric surgery patients who are close to their surgery date as well as those who completed bariatric surgery within 18 months. Participants will not be consented until surgery completion. Patients will be recruited via U.S. mail, as well as at support groups/classes and clinic appointments. We anticipate that of the ~25 surgeries conducted monthly, recruitment will take approximately 6 months to recruit 80 patients on a rolling basis. We will run two, possibly three, biweekly groups simultaneously if needed to accommodate patients available for day or evening groups. The primary outcome will be the difference in quality of life postoperatively, between groups, as well as differences in psychosocial functioning (mood, eating behaviors) and adherence (diet, physical activity, appointments). Outcomes will be assessed at time of enrollment and then at after completion of 8 treatment sessions (BI group). Final outcomes assessments will be distributed to BI and UC patients at the same time to maintain consistent data collection intervals between the groups. Secondary outcomes will include patient satisfaction.

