A member of the research team will remind the participants that randomize to the Intervention Group the day before each session either via phone or email (if participant chooses email communication they will provide the study team with their email address).

Should any participant express significant psychiatric distress in group, such as emotional reactions to weight loss or how relationships are affected, the group leader (a clinical psychology resident) will assess the participant immediately after group and consult with the study PIs ([name] or [name]). The group leader and study PI(s) will refer the participant for further treatment as appropriate. The group leader may also ask disruptive participants to leave group at any time.

Usual Care:

Participants randomized to usual care will complete surveys at postoperative clinic visits or if necessary, via mail. Upon study completion, patients randomized to usual care will be offered the 8 sessions provided to the BI group. This group will run after all study data have been collected.

Table 4. Compensation and Reimbursement

Behavioral Intervention Group	Compensation(Surveys) Reimbursement (Sessions)	Usual Care Group	Compensation (Surveys)
Baseline Surveys	\$50	Baseline Surveys	\$50
Session 1	\$15	N/A	N/A
Session 2	\$15	N/A	N/A
Session 3	\$15	N/A	N/A
Session 4	\$15	N/A	N/A
Session 5	\$15	N/A	N/A
Session 6	\$15	N/A	N/A
Session 7	\$15	N/A	N/A
Session 8	\$50	Final Surveys	\$50
TOTAL	\$205	TOTAL	\$100

Measures:

Surveys for Aims 1-2 will be administered to all participants at post op baseline (within two weeks of signing consent) and then at the completion of the 8 treatment session timeframe for both the BI and UC groups. Aim 3 measures of feasibility and satisfaction will be administered to BI participants only and at one time point, at study conclusion. Demographic, surgical and medical information will be collected from the EMR including weight (kg), height (cm), age at enrollment, sex, race/ethnicity, surgery type, insurance status, diagnoses and medication.

(Surveys are attached).

1. SF-36, Health-Related Quality of Life (HRQoL, primary outcome): As part of the Medical Outcomes Study (MOS), RAND developed the 36-Item Short Form Health Survey (SF-36). The SF-36 is a set of valid, reliable³⁴⁻³⁶, and easily administered QoL measures that have been used in obese populations^{37,38}.

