6.8.1 Statistical Analysis Plan

Randomization will be conducted using randomization schema generated by the Biostatistician. Randomization to UC or BI will occur following consent. It is plausible that yellow light patients may experience greater benefit from the intervention. We will examine the comparability of demographics characteristics between two groups at baseline. If baseline demographic factors are not balanced between the two groups, we will then adjust for these factors during final analyses.

The primary outcomes will be the difference in mean HRQoL scores (emotional scale) as assessed by the SF-36 between the BI and UC groups at postoperative month 4 (assessment time frame will be postoperative month 1 to month 4). Continuous variables will be analyzed using independent t-tests. We will evaluate the appropriate assumptions using Shapiro–Wilk or Kolmogorov–Smirnov tests (normality) and a Brown–Forsythe test or a Q–Q plot (homogeneity of variance). Should the normality assumption be violated, we will then attempt transformations. If necessary, ANCOVA will be used to control for wave (1 vs 2) or other baseline covariates.

Secondary outcomes include differences between groups in the remaining HRQoL scales. Similar methods as described for the primary outcome will be used for the secondary outcomes. Additionally, within group analyses (secondary) will use paired t-tests. Categorical variables will be analyzed by chi-squared tests.

We will conduct intent-to-treat analysis to determine differences in primary and secondary outcomes using data from all randomized participants. Missing data will be handled using multiple imputation⁵⁵. We will also conduct sensitivity analyses such as best and worst case analyses⁵⁶.

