6.8.2 Statistical Power and Sample Size Considerations

Previous research⁵⁴ indicates that bariatric surgery patients report mean (SD) SF-36 subscale scores before and after surgery of:

	Preoperative	Postoperative	Effect Size
Role - Emotional	74.9 (34.4)	92.3 (22.1)	0.56 SD
Mental Health	70.5 (17.4)	74.6 (18.9)	0.2 SD
Mental Health Composite Score	48.9 (10.1)	52.1 (8.4)	0.3 SD

We aim for a difference of 2/3 standard deviation in scores between groups at 4 months postoperatively. A sample size of 40 participants per group will have 83% power to detect an effect size of 2/3 SD using a two group t-test with a 0.05 two-sided significance level. If the effect size is small than 2/3 SD, we will still be able to assess the level of confidence on the observed differences that will be used to design a large study. When the sample size in each group is 40, a two-sided 95.0% confidence interval for the difference of two means in mental health composite score will extend 4.4 from the observed difference in means, assuming that the common standard deviation is known to be 10.1 and the confidence interval is based on the large sample z statistic.

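### Change within the BI arm alone is a secondary outcome tested by paired t-test and not labelled descriptive, so it could be misread as efficacy

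*Combined protocol and SAP*

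**What the plan says.** Section 4.1 (Hypothesis) states: "As secondary outcomes, we will evaluate within group changes (BI group) from enrollment to completion of 4-month intervention program". Only the BI arm is named. Section 6.8.1 (Statistical Analysis Plan) supplies the test: "within group analyses (secondary) will use paired t-tests". Neither section calls the result descriptive or says how a significant change is to be interpreted. Section 6.7 (Secondary Endpoints) does not list within-group change.

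The control arm provides the same data. In section 6.5, under Measures, "Surveys for Aims 1-2 will be administered to all participants at post op baseline" and again "at the completion of the 8 treatment session timeframe for both the BI and UC groups". Section 6.1 adds: "Final outcomes assessments will be distributed to BI and UC patients at the same time".

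The main analysis is between arms. Section 6.8.1 says "The primary outcomes will be the difference in mean HRQoL scores (emotional scale) as assessed by the SF-36 between the BI and UC groups", and it compares the remaining quality-of-life scales between groups as well. Specific Aims 1 and 2 define efficacy relative to UC. Continuous outcomes are compared by independent t-test; ANCOVA is allowed only if needed, for wave or other baseline covariates.

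**The concern.** A paired test in one arm asks whether scores changed, not whether the programme changed them. Recovery after surgery, a time trend and regression to the mean all enter the same mean difference, and the test has no means of removing them.

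Early recovery is a realistic source of drift for some participants. Patients approached before surgery consent at their first postoperative appointment and then complete baseline surveys (section 6.3), and section 6.8.1 describes an assessment window of about months 1 to 4 after surgery.

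What is at stake is interpretation. The between-arm test is powered for a large effect, 2/3 SD (section 6.8.2), so a null BI-UC result beside a significant BI-only improvement is a plausible outcome. Section 4 says the data will support grant applications and manuscripts. The plan has no rule to stop the BI-only result being presented there as evidence that the programme works.

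**Working it through.** **1. The plan's own figures.** Inputs from section 6.8.2: 40 per arm, effect 2/3 SD, two-sided alpha 0.05, stated power 83%. The two-sample noncentral t gives 83.8% and the normal approximation 84.6%, so the stated power reproduces within 2 points. The stated confidence interval half-width of 4.4 also reproduces: 1.96 × 10.1 × √(2/40) = 4.43.

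**2. Paired test with no programme effect.** Let δ be the drift in SD units of the score (equal SD at both times) and r the baseline-to-follow-up correlation. Then

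- standardised change: dz = δ / √(2(1 − r))
- noncentrality: λ = dz × √n, with n = 40 and 39 degrees of freedom
- chance of significance: the probability that |T(λ)| exceeds the two-sided 5% critical value.

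The documents give neither δ for a postoperative baseline nor r. Both are assumptions. The 0.56 SD row is the Role-Emotional effect size printed in section 6.8.2.

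| Drift | r = 0.3 | r = 0.5 | r = 0.7 |
|---|---|---|---|
| 0 | 5.0% | 5.0% | 5.0% |
| 0.1 SD | 8.2% | 9.5% | 12.5% |
| 0.2 SD | 18.1% | 23.5% | 35.7% |
| 0.3 SD | 34.6% | 45.7% | 66.6% |
| 0.56 SD | 83.1% | 93.2% | 99.4% |

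Example: δ = 0.3 and r = 0.7 give dz = 0.3/√0.6 = 0.387 and λ = 0.387 × √40 = 2.45, hence 66.6%. No dropout rate is stated; with 32 complete pairs as an illustration, the range for 0.1 to 0.3 SD is 7.5% to 56.5%.

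**3. Scaling to the section 6.8.2 table.** That table gives mean (SD) before and after surgery: Role-Emotional 74.9 (34.4) to 92.3 (22.1), Mental Health 70.5 (17.4) to 74.6 (18.9), Mental Health Composite 48.9 (10.1) to 52.1 (8.4). The SD of change is √(s1² + s2² − 2·r·s1·s2). For Role-Emotional at r = 0.5 this is √(1183.4 + 488.4 − 760.2) = 30.2, so dz = 17.4/30.2 = 0.58. The chance of significance with no programme effect, for r from 0.3 to 0.7, depends on how much of the tabulated change falls within follow-up:

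| Share of change | Role-Emotional | Composite | Mental Health |
|---|---|---|---|
| All | 87–99% | 43–77% | 22–43% |
| Half | 34–59% | 15–27% | 9–15% |
| A quarter | 12–19% | 7–10% | 6–7% |

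**4. Between-arm tests under the same drift.** Simulation with 20,000 trials, 40 per arm, r = 0.5, equal drift of 0.2, 0.3 or 0.56 SD in both arms and no programme effect:

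| Drift | BI-only paired | BI-UC, final score | BI-UC, change score |
|---|---|---|---|
| 0.2 SD | 23.8% | 5.2% | 4.9% |
| 0.3 SD | 45.5% | 5.2% | 5.1% |
| 0.56 SD | 93.2% | 5.3% | 5.0% |

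The excess comes from the missing control, not from the data or the scale.

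**The case against.** The strongest reply is that the plan never says it will treat a within-BI change as efficacy. Aims 1 and 2, the primary outcome and the remaining quality-of-life scales are all BI against UC. Section 6.8.1 introduces the paired tests as an addition, and section 6.7 leaves them out. This stands. A reader might infer that the plan will credit recovery to the programme, or that the control arm goes unused; the documents support neither reading.

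The second reply concerns the section 6.8.2 table. A reader might take it as proof that scores keep rising during this trial's follow-up. It does not show that: its changes span the operation, whereas baseline here follows surgery by anything from the first visit to 18 months (sections 6.2.2 and 6.3). Those changes are best read as an upper range. The documents give no mix of early and late entrants. In late entrants drift could be nil or downward and could hide a benefit; section 3 describes weight regain beginning at one year in some gastric bypass patients. Nor is entry restricted to low scorers, which limits regression to the mean. All of this stands, and it is why the size is given as a range.

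A reader might also expect several scales to reach significance by drift alone. That cannot be calculated, because the drift and correlation across scales are not given.

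Third, within-arm change is useful in a pilot. That is a reason to keep it as a description, so outright deletion is not needed. It is not a reason to test it as an outcome.

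**Conclusion.** The point holds as a gap in interpretation, of low to moderate weight. A named secondary outcome rests on an uncontrolled test and has no stated rule for reading it, and sections 4.1, 6.7 and 6.8.1 disagree on whether it is a secondary outcome at all. The primary between-arm comparison is not invalidated.

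For an assumed drift of 0.1 to 0.3 SD, correlation 0.3 to 0.7 and 40 complete pairs, the BI-only test is significant in about 8% to 67% of trials with no programme effect. If only a quarter of the tabulated pre-to-post changes falls within follow-up, the figure is 6% to 19%, depending on the scale. With no drift it is the nominal 5%. Figures above 80% require the whole Role-Emotional change, or drift of similar size, to occur after a postoperative baseline, which the documents do not support.

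**What to change.** - In sections 4.1 and 6.8.1, replace the BI-only paired tests with mean change and 95% CI for both arms, labelled descriptive.
- State in 6.8.1 that efficacy conclusions come only from the BI-UC difference.
- Estimate that difference by ANCOVA adjusted for the baseline score of the same scale, as the planned analysis in place of the unadjusted t-test and not only if needed.
- Align sections 4.1, 6.7 and 6.8.1 on whether within-group change is a secondary outcome.

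The cost is wording and one model specification. Both arms already complete the surveys at both times, so no visit, patient or data item is added. The adjustment should also improve precision: the variance of the difference falls by a factor of about 1 − r². The 4.43-point half-width would become about 4.43 × √0.91 = 4.2 at r = 0.3, 4.43 × √0.75 = 3.8 at r = 0.5 and 4.43 × √0.51 = 3.2 at r = 0.7, again with r assumed.

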6.8.2 Statistical Power and Sample Size Considerations

Previous research⁵⁴ indicates that bariatric surgery patients report mean (SD) SF-36 subscale scores before and after surgery of:

	Preoperative	Postoperative	Effect Size
Role - Emotional	74.9 (34.4)	92.3 (22.1)	0.56 SD
Mental Health	70.5 (17.4)	74.6 (18.9)	0.2 SD
Mental Health Composite Score	48.9 (10.1)	52.1 (8.4)	0.3 SD

We aim for a difference of 2/3 standard deviation in scores between groups at 4 months postoperatively. A sample size of 40 participants per group will have 83% power to detect an effect size of 2/3 SD using a two group t-test with a 0.05 two-sided significance level. If the effect size is small than 2/3 SD, we will still be able to assess the level of confidence on the observed differences that will be used to design a large study. When the sample size in each group is 40, a two-sided 95.0% confidence interval for the difference of two means in mental health composite score will extend 4.4 from the observed difference in means, assuming that the common standard deviation is known to be 10.1 and the confidence interval is based on the large sample z statistic.

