5 PRELIMINARY DATA

Modifiable psychosocial risk factors, including mood disorders⁴, likely contribute to difficulties with postoperative compliance as psychiatric disorders are associated with general medical non-compliance^{14,15}. In the GHS bariatric surgery research database (N=3,695), 43% (n=1,580) have at least one psychiatric diagnosis before surgery (ICD-10) and 56% (n=2,045) took at least one psychiatric medication (Table 1). While the rates of psychiatric disorders in bariatric surgery patients are high, particularly depression and anxiety, few programs provide psychological support for patients after surgery beyond monthly support groups.

Table 1: Select psychiatric diagnoses from the EMR in GHS bariatric patients before surgery (N=3,695)

Depression (311)	1,005	27.20%
Anxiety (300)	317	8.60%
Non-dependent Drug Abuse (305)	226	6.10%
Episodic Mood Disorder (296)	196	5.40%
Adjustment Reaction (309)	145	3.90%
Personality Disorders (301)	23	<1.0%
SSRI/serotonin modulators	1,574	42.60%
SNRI	517	14.00%
Misc. Antidepressant	346	9.50%
Tricyclic Agents	267	7.20%
Benzodiazepines	121	3.30%

At GHS, patients considering bariatric surgery undergo preoperative psychological evaluations to evaluate their readiness for surgery. All patients are then given a “traffic light” status (red, yellow, or green) according to their readiness. Patients given a “green” light are cleared for surgery, while “yellow” light patients (~25%) have preoperative milestones that require further attention before surgery (i.e., preoperative weight gain, psychiatric issues that require collateral information or referrals to mental health treatment, and difficulty adopting dietary changes before surgery). We believe that the proposed intervention may be particularly effective in patients that initially received a yellow light, but we will include both initial green and yellow light patients for this pilot study and then evaluate outcomes by light status as a secondary analysis

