6.2.2 Inclusion Criteria

- Age 18-65 years
- BMI \geq 35 kg/m² at time of surgery

- Primary bariatric surgery completion \leq 18 months
- Understanding of informed consent

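### If the primary score is Role-Emotional and usual care scores near the plan's own 92.3, a 2/3 SD benefit would pass the assumed scale maximum, so the 83% power does not hold for that score

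*Combined protocol and SAP*

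**What the plan says.** Section 6.8.1 defines the primary comparison: "The primary outcomes will be the difference in mean HRQoL scores (emotional scale) as assessed by the SF-36", BI against UC, by independent t-tests. It does not say which SF-36 score the emotional scale is.

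Section 6.8.2 opens with a table of earlier results, which it says "indicates that bariatric surgery patients report mean (SD) SF-36 subscale scores before and after surgery of" three scores. After surgery these are Role-Emotional 92.3 (SD 22.1), Mental Health 74.6 (18.9) and the mental health composite 52.1 (8.4). Before surgery Role-Emotional is 74.9 (34.4). The sizing follows: "We aim for a difference of 2/3 standard deviation in scores between groups at 4 months postoperatively". The power claim comes next: "A sample size of 40 participants per group will have 83% power to detect an effect size of 2/3 SD". The test behind it is a t-test of BI against UC at the two-sided 5% level. The section adds that a smaller effect would still inform a larger study. It gives a confidence-interval half-width of 4.4, for the composite only.

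Both arms have already had surgery: section 6.1 defers consent until after the operation, and section 6.2.2 admits patients up to 18 months later. Sections 6.2.2 and 6.2.3 set no threshold for distress or poor quality of life. Section 5 adds that "we will include both initial green and yellow light patients for this pilot study".

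**The concern.** A standardised effect size says nothing about whether the score has room for the effect. Only one row of the 6.8.2 table carries the word emotional, and its postoperative mean is already high. Both arms are postoperative and entry is not restricted to patients who are doing badly, so that row is the only guide the plan gives to where UC will score on it. If UC sits near 92.3, recovery after surgery has used up most of the scale before the program can add anything.

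Two things are at stake. The power attached to the primary score would describe an effect that cannot happen on it. And section 4 says that the data will support later grant applications: a null result produced by a ceiling could discourage a larger trial, or that trial could be sized on an unattainable difference.

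**Working it through.** **Inputs.** From 6.8.2: 40 per group, two-sided 0.05, two-group t-test, target 2/3 SD, postoperative Role-Emotional 92.3 (SD 22.1). Assumed, because the documents do not state it: Role-Emotional runs from 0 to 100.

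**1. The plan's own figures.** Noncentral t power for d = 2/3 with 40 per group is 83.8%, in line with the stated 83%. The half-width for the composite is 1.96 × 10.1 × √(2/40) = 4.43, in line with 4.4. The arithmetic is sound for a generic 2/3 SD.

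**2. The target in points.** 2/3 × 22.1 = 14.7. With UC at 92.3, the BI mean would have to be 92.3 + 14.7 = 107.0, which is 7.0 points above the assumed maximum. The preoperative SD of 34.4 would push it further, to 92.3 + 22.9 = 115.2. That SD does not suit this comparison: on a 0 to 100 scale with mean 92.3, no SD can exceed √(92.3 × 7.7) = 26.7.

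**3. The room available.** 100 − 92.3 = 7.7 points.

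**4. Power for 7.7 points, under two SD assumptions.**

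| Assumption | SD used | d | Power, 40 per group |
|---|---|---|---|
| SD 22.1 in both arms | 22.1 | 7.7/22.1 = 0.35 | about 34% |
| Every BI patient at 100 (BI SD 0) | √(22.1²/2) = 15.6 | 7.7/15.6 = 0.49 | about 59% |

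The second row is the only way to gain the full 7.7 points. The t formula is approximate there, because one arm has no variance. Simulation with two discrete score distributions for UC, each with mean 92.3 and SD 22.1, gave roughly 66% to 73%. Every figure is below 83%, and 0.49 is below 2/3.

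**5. When the target would fit.** With SD 22.1, 14.7 points stay within the scale only if the UC mean is at or below 100 − 14.7 = 85.3. At exactly 85.3, every BI patient would have to reach the maximum.

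**6. The other rows.** Mental Health: 74.6 + 2/3 × 18.9 = 87.2. Composite: 52.1 + 2/3 × 8.4 = 57.7, or 58.8 with SD 10.1. Neither shows a comparable conflict.

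**The case against.** The strongest reply is that the conflict rests on three things the documents do not settle. The emotional scale is never defined as Role-Emotional, and the one precision statement tied to a score uses the composite, where there is room. The scale maximum is not given. And 92.3 comes from earlier research with no stated time since surgery, whereas this trial enrols from the first postoperative visit up to 18 months, so UC may score lower. All three stand as conditions on the point. They do not remove it: the plan offers no other row for that word, and no reason to expect a UC mean as low as 85.3.

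A second reply is that this is a pilot and 6.8.2 expects that the effect may be smaller. That softens the consequence, but the plan's fallback precision covers the composite only, and the 83% is still stated without limit to a score.

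Three stronger readings are tempting and should be resisted:

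- A reader might take 34% as the most power the trial could have on Role-Emotional. It assumes SD 22.1 in both arms, and BI variance must shrink as patients approach the maximum.
- A reader might infer that a null on Role-Emotional would say nothing about the program. With about 59% power or somewhat more in the extreme case, a null would be weak evidence, not none.
- A reader might conclude that the composite should become primary and carry the 83%. The documents do not support that step: 6.8.2 lists only 0.3 SD for the whole change with surgery on that score, so 2/3 SD for a support program would need its own justification.

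**Conclusion.** The point holds conditionally. If the emotional scale means Role-Emotional, UC scores near 92.3 with SD 22.1, and the maximum is 100, the 2/3 SD target (14.7 points, BI mean 107.0) cannot occur, and the stated 83% does not hold for that score. The attainable difference is then at most 7.7 points, with power of about 34% to 59% by the t-test formula depending on how far BI variance falls, and still below 83% by simulation in the extreme case. The conclusion fails if UC averages about 85.3 or lower, if the scale maximum is 107.0 or more, or if the composite was intended. The 83% is not an arithmetical error; it has not been tied to a score that can accommodate the effect. It is worth correcting, because it is the power stated for the primary comparison.

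**What to change.** In 6.8.1 and 6.8.2, name the exact SF-36 score that is primary. Give the target difference in points, with the assumed UC mean, SD and scale maximum, so that a reader can see that it fits.

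If the score is Role-Emotional, withdraw the 83% for it. State the attainable difference (about 7.7 points or less if UC is near 92.3) and recompute power under stated SD assumptions for each arm.

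Plan to report the proportion of patients at the scale maximum, by arm, at baseline and follow-up, so that a null on Role-Emotional is read as weakly informative.

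Whether to change the primary score is the sponsor's choice and should be made before outcome data are seen. If the composite is chosen, the 83% should not move with it unless 2/3 SD is justified there.

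The cost is wording in two sections and one descriptive table. The SF-36 is already collected in both arms at both time points, so no new data or patients are needed. The price is a less favourable stated power if Role-Emotional stays primary. A change of primary score would be a substantive amendment, not just wording.
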